The first chart review will take place after obtaining patients' consent to participate in this study. Patient data will be abstracted within 28 days after obtaining informed consent. The data will be abstracted from the medical chart and will include relevant medical history, data recorded in the year prior to cladribine tablet initiation, and data recorded between the date of treatment initiation with cladribine tablets and the study enrolment date ([Table 1](#) and [Section 9.3](#)). In addition, the patient's general practitioner may be contacted by the principal investigator or a member of the site team to obtain information regarding medical history and concomitant medications.

The second chart review will be conducted approximately 1 year after enrolment (within a window of 14 days from a year after the enrolment date). This second chart abstraction will collect data recorded between the enrolment date and the date of the second data abstraction ([Table 1](#) and [Section 9.3](#)).

The data to be collected are routinely collected information per clinical practice, including demographic data, disease characteristics (relapse reports, Expanded Disease Severity Scale [EDSS] scores, MRIs, and lymphocyte counts, as available), treatments (cladribine tablets, other DMTs for MS, and COVID-19 vaccines), medical history, and selected AEs.

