### 9.1.2.2 Secondary

- Proportion of patients who remain relapse-free in each year and at 4 and 5 years after initiation of cladribine tablet treatment
- Time from cladribine tablet initiation to first relapse
- Proportion of patients who discontinued cladribine tablets and reasons for discontinuation
- Subsequent DMTs (none or by DMT type) received after cladribine tablets discontinuation/treatment completion up to 5 years after cladribine tablets initiation
- Disability assessed by the EDSS at treatment initiation and start of treatment Year 2

The EDSS is a neurological assessment to evaluate disability in patients with MS, performed by the physician. The annual EDSS at cladribine tablet treatment initiation and start of treatment Year 2 will be recorded, where available in the patients' notes. EDSS is routinely collected as part of standard care in the UK as part of the annual assessment required for continuation of treatment.

- Proportion of patients with disability progression confirmed over 6 months, assessed by the EDSS, at 2 years after cladribine tablet treatment initiation

An EDSS progression is defined as an increase in the EDSS scale as follows:

- If the EDSS score at cladribine tablet initiation is 0, the increase must be  $\geq 1.5$  units
- If the EDSS score at cladribine tablet initiation is  $\geq 0.5$  or  $\leq 4.5$ , the increase must be  $\geq 1.0$  units
- If the EDSS score at cladribine tablet initiation is  $\geq 5.0$ , the increase must be  $\geq 0.5$  units.

A confirmed disability progression is defined as EDSS progression (as defined above) confirmed after 6 months.

- Rates of selected, identified, and potentially clinically important AEs, including:

- grade 3 lymphopenia
- grade 4 lymphopenia
- herpes infections
- serious infections (infections for which a hospitalisation is initiated or extended)
- opportunistic infections (new onset or reactivation of latent infection)
- malignancies

These AEs will be reported from the date of cladribine tablet initiation and will be described overall and by most recent prior DMT subgroups (DMT naïve, prior platform treatment, prior high-efficacy cell-depleting treatment, and prior high-efficacy non-depleting treatment).

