#### **9.2.1.1                            Inclusion Criteria**

For inclusion in the study, all of the following inclusion criteria must be fulfilled:

1. At least 18 years of age at cladribine tablet treatment initiation
2. Physician diagnosis of HDA-RRMS as defined by clinical or radiological features
3. Treatment initiation with cladribine tablet monotherapy on or after 22 August 2017 and at least 3 years before enrolment
4. Completion of Year 1 treatment of cladribine tablets (Week 1 and Week 2 treatment, per recommended dose in Year 1: 1.75 mg/kg body weight, cumulatively)
5. Provide written informed consent to participate in the study

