**Table 1 Schedule of Study Events**

Data	Enrolment (Day 1)	Chart Review 1 (Day 1)	Chart Review 2 (Year 1)
Window	-	+28 days	±14 days
Informed consent	X		
Eligibility criteria		X	
Demographic data		X	
Medical history and comorbidities		X	
Medication history		X	
MS disease history		X	

Data	Enrolment (Day 1)	Chart Review 1 (Day 1)	Chart Review 2 (Year 1)
Prior disease-modifying therapies		X	
Treatment with cladribine tablets		X	
Subsequent disease-modifying therapies		X	X
COVID-19 vaccines		X	X
Clinical confirmed relapses		X	X
Annual EDSS scores		X	X
MRI data		X	X
Lymphocyte levels		X	X
Selected adverse events		X	X

EDSS: Expanded Disability Status Scale; MRI: Magnetic Resonance Imaging; MS: Multiple Sclerosis

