## **9.3 Variables**

- Demographic data at cladribine tablet initiation: Gender, age, height and weight measurements on or nearest to the date of initiating cladribine tablets in the year prior to treatment initiation
- Medical history and comorbidities at cladribine tablet initiation: All relevant medical history and comorbidities in the year prior to initiation with cladribine tablets (both past and ongoing comorbidities at date of initiation with cladribine tablets will be collected)
- Medication history at cladribine tablet initiation: Relevant medications taken in the year prior to initiation with cladribine tablets
- MS disease history: Date of initial MS diagnosis and type of MS at cladribine tablet initiation
- Prior DMTs: Any DMT for MS, taken since initial MS diagnosis and prior to initiating treatment with cladribine tablets, including starting date, end date, and dosage. The most recent DMT taken prior to initiation with cladribine tablets will be categorised in subgroups, as defined in [Section 9.7.1.1](#):
  - naïve to DMT
  - prior platform therapy
  - prior high-efficacy cell-depleting treatment

- prior high-efficacy non-depleting treatment
- Treatment with cladribine tablets: date of initiation of each treatment course, dose, potential date of discontinuation of treatment and reason for discontinuation, if applicable.
- Subsequent DMTs: Other DMTs for MS initiated after treatment with cladribine tablets will be recorded, including the date of initiation, potential discontinuation date, and dosage.
- COVID-19 vaccines: Vaccines for coronavirus disease 2019 (COVID-19) attributable to severe acute respiratory syndrome coronavirus 2 (SARS-CoV-2) administered in the years after initiation of cladribine tablets (until end of observation period) will be recorded.
- Course of disease:
  - clinician confirmed relapses: Each relapse that occurred in the year prior to treatment initiation with cladribine tablets and each year after will be recorded with the onset date (at least month and year)
  - annual EDSS scores: At start of cladribine tablet treatment Year 1, at the start of cladribine tablet treatment Year 2, and 2 years after cladribine tablet treatment initiation
  - MRI data (upon availability): T1 gadolinium enhancing lesions, T2 lesions (new/enlarging compared to a previous scan)
- Lymphocyte levels: At initiation of cladribine tablet treatment and during the years after, where available.

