#### Secondary Outcome Analysis

The proportion of patients who remain relapse-free in each year after treatment initiation (among patients active at start of each year), at 4 years after treatment initiation and at 5 years after treatment initiation (among patients with 5 years observation time available), and the time from cladribine tablet initiation to first relapse will be described using Kaplan-Meier method. Kaplan-Meier survival curve will be plotted (overall and by most recent prior DMT subgroup) and a table with the probabilities of remaining relapse-free in each year after initiation of treatment will be produced.

The proportion of patients who discontinued cladribine tablets and reasons for discontinuation will be summarised using descriptive statistics.

Subsequent DMTs (none or by DMT type) received after treatment with cladribine tablets will be described up to 5 years after cladribine tablet initiation. The proportion of patients who did not receive any other DMT up to a total of 4 years and up to a total of 5 years (among patients with 5 years observation time available) after cladribine tablet treatment initiation will be analysed using descriptive statistics. Depending on the availability of data and the missing data pattern, a survival analysis may be performed to account for loss to follow-up patterns.

The annual EDSS scores at treatment initiation and start of cladribine tablet treatment at Year 2 will be summarised using descriptive statistics. The proportion of patients with disability progression confirmed over 6 months at 2 years after cladribine tablet initiation will be summarised using descriptive statistics.

The number and percentages of patients with AEs will be reported, and the number of AEs itself. The incidence rates of AEs will be summarised by system organ class and preferred term using the Medical Dictionary for Regulatory Activities (MedDRA). Additional summaries will be presented by severity. The AEs will be reported overall, and as stratified in the last prior MS DMT subgroups (as defined in [Table 2](#)).

CCI

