9.6 Time Window

For analyses conducted at yearly intervals (e.g. relapse rate at each year) the date of the event will be assigned an analysis time-point according to [Table 1](#):

Table 1. Time windows for relapses analysis

Time-point	Study day	
	From	To
Year -1	-365	-1
Year 1	84*	365
Year 2	366	731
Year 3	732	1096
Year 4	1097	1461
Year 5	1462	1826

*Relapses occurred within the induction period window of 12 weeks (84 days) will not be included in the main analysis. Sensitivity analyses will be repeated changing Year 1 interval to (56 to 365 days) and (1 to 365 days) respectively.

For EDSS analysis on disability progression the [Table 2](#) will be followed:

Table 2. Time window for EDSS analysis

Time-point	First assessment		
	Study day		
	From	Mid-point	To
Baseline	-60	-	1
Year 2 (treatment start date) OR Year 2	183	365	548

The closer assessment to the Year 2 treatment start date will be used. If the patient does not receive any treatment at Year 2, [Table 2](#) time-window will be used to derive the Year 2 EDSS assessment. The confirmatory EDSS score assessment (used to confirm disability progression) will be selected in the (+91; +272) days interval from the 'Year 2' assessment date. In case of multiple assessments within this window the closer to +182 days from the 'Year 2' assessment date will be picked.

In case of multiple assessments at the same distance of the mid-point the earliest one will be considered for the analysis. All measurements will be listed.

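### SAP 9.6 takes the disability-progression EDSS at nominally about 1 year, SAP 14.2.4 reports it as a 2-year result, and the protocol's own 2-year EDSS has no window

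*SAP*

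**What the plan says.** **Protocol.** The secondary outcome analysis (9.7.3) states that the proportion of patients with "disability progression confirmed over 6 months at 2 years after cladribine tablet initiation will be summarised using descriptive statistics". Section 9.1.2.2 adds: "A confirmed disability progression is defined as EDSS progression (as defined above) confirmed after 6 months". It states no tolerance around the 6 months. Section 9.3 lists a score at the start of treatment Year 1 and then two later ones: "at the start of cladribine tablet treatment Year 2, and 2 years after cladribine tablet treatment initiation". So the 2-year EDSS is a different item from the one at the start of the second course.

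**SAP 9.6, Table 2.** There is one post-baseline row, labelled 'Year 2', running from Day 183 to Day 548 with mid-point Day 365. The text below it takes the score nearest the start of the Year 2 course. For patients with no Year 2 course it uses the Table 2 window. The confirming score "will be selected in the (+91; +272) days interval" counted from that first score. If several qualify, the one nearest +182 days is used.

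**SAP 14.2.4** reports the number and percentage with 6-month-confirmed progression at Year 2 after initiation, and puts all other EDSS scores in a listing. **SAP 7** declares no departure from the protocol's analyses.

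**The concern.** The label 'Year 2' does two jobs. In the EDSS table it means the start of the second treatment year, nominally 1 year after initiation. In SAP 14.2.4 and in the protocol outcome it reads as 2 years after initiation. For relapses, Table 1 of the same SAP section ends Year 2 at Day 731. A reader of the report would take a percentage based on worsening at about 1 year for a 2-year result.

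The confirmation rule adds a second problem. The protocol says that "EDSS is routinely collected as part of standard care in the UK as part of the annual assessment required for continuation of treatment". Annual scores are about 12 months apart, but the rule accepts only 3 to 9 months. For a patient on schedule, neither post-baseline EDSS named in protocol 9.3 can then confirm progression. Confirmation depends on whether an extra score happens to exist in between.

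At stake is a named secondary outcome, reported overall and in four prior-DMT subgroups.

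**Working it through.** **Inputs.** SAP 9.6: first-score window Day 183-548, mid-point 365; confirmation +91 to +272 days, target +182. SAP 9.4: 30.4375 days per month, 365.25 per year. Protocol 9.2.2: the Year 2 course may start as late as 18 months after initiation. Protocol 9.2.1.1: initiation "on or after 22 August 2017 and at least 3 years before enrolment". Protocol 9.5: 90 to 200 patients. Assumption: the 2-year EDSS falls at about Day 731 (2 × 365.25 = 730.5; SAP Table 1 ends Year 2 at Day 731).

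**1. The SAP's own figures.** 6 × 30.4375 = 182.6 days, which gives the +182 target; 182 − 91 = 91 and 182 + 90 = 272. 183/30.4375 = 6.01, 365/30.4375 = 11.99 and 548/30.4375 = 18.00 months. The table therefore describes a 12-month score (± 6 months) with confirmation at 6 months (± 3 months).

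**2. Can the 2-year EDSS be the progression score?** 731 − 548 = 183 days past the last day of the Table 2 window, so under Table 2 it cannot.

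**3. Can it confirm an on-schedule first score?**

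| First score | Accepted for confirmation | Day 731 is late by |
|---|---|---|
| Day 365 | 456 to 637 | 731 − 637 = 94 days |
| Day 366 | 457 to 638 | 731 − 638 = 93 days |

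The actual gap is 365-366 days (11.99-12.02 months) against a ceiling of 272 days (8.94 months). Using Day 730, or treating the limits as exclusive, moves the shortfall only within 92-95 days.

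**4. Which first scores can Day 731 confirm?** Earliest: 731 − 272 = Day 459 (15.1 months). Latest: 731 − 91 = Day 640. If Table 2's limits bind, this leaves Day 459-548, or 548 − 459 + 1 = 90 of the window's 548 − 183 + 1 = 366 days. For a Year 2 course starting at 18 months, 366 + 183 = Day 549 and 731 − 549 = 182 days, exactly on target. The same 2-year score is thus usable after a delayed course and unusable after an on-time one.

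**5. The lower limit.** 91/30.4375 = 2.99 months. If the only later score is at +91 days, it passes; +182 only decides between several.

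**6. Are later scores available?** Protocol Table 1 marks "Annual EDSS scores" at both chart reviews, and section 9.1.1 says: "This second chart abstraction will collect data recorded between the enrolment date and the date of the second data abstraction". Enrolment is at least 3 × 365.25 = 1095.75 days after initiation, so anything recorded between enrolment and Chart Review 2 is at about Day 1096 or later. None of the three scores in protocol 9.3 falls there. Either later scores are collected or the Table 1 entry has no content; the protocol does not say which.

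**7. Scale.** With the FAS as denominator, one reclassified patient moves the overall percentage by 1/200 = 0.5 to 1/90 = 1.1 points, and by more within a subgroup. How many patients are affected cannot be derived.

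**The case against.** Several points on the other side stand.

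- First scores are not all at 1 year. Table 2 allows 6 to 18 months, and for patients with a Year 2 course the text does not say whether its limits apply at all. The 93-94 days is the nominal case.
- A tolerance is sensible in routine-care data. The window is roughly symmetric about +182, the nearest score is preferred, and the protocol sets no tolerance to breach. The 3-month interval is the edge of the rule, not its aim.
- 'At 2 years' might mean confirmed by about 2 years. Even so, the rule ignores worsening first seen after the selected score and rejects an on-schedule 2-year EDSS as confirmation.
- Part of the fault lies in the protocol. Section 9.1.2.2 summarises EDSS only at initiation and the start of Year 2, section 9.3 adds a 2-year score, and no section names a score that could confirm that one.
- SAP 9 already keeps missing observations as a separate category in the denominator, and SAP 9.6 lists all measurements. Neither says how progression without a confirming score is classified.

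A reader might infer more than this: that no progression can be confirmed, that the 2-year EDSS is never usable, that only a quarter of patients (90/366 = 24.6%) can be confirmed by it, or that the percentage is biased in a known direction. The documents support none of these. An extra EDSS on about Day 456-638 would confirm an on-schedule first score, and a delayed first score can be confirmed at 2 years. The 24.6% is a share of days, not of patients, and assumes that Table 2's limits bind.

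**Conclusion.** The point holds as a mismatch of label and window. SAP 9.6 and 14.2.4 present progression first seen at nominally about 1 year as a 2-year outcome. The protocol's 2-year EDSS has no window and, for a first score on Day 365-366, comes about 93-94 days too late to confirm. Worsening first recorded after the selected score is not counted. A single score 2.99 months later can pass as 6-month confirmation. SAP 7 declares none of this.

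The day counts assume an on-time Year 2 course and a 2-year EDSS at about Day 731. The effect on the percentage cannot be sized, because the documents give no distribution of EDSS dates. Its direction is also open: lost confirmations and uncounted later onset lower the figure, while the short lower limit can raise it by counting transient worsening. The outcome is secondary and descriptive with no hypothesis test, so this should be fixed but does not threaten the primary outcome.

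**What to change.** 1. In SAP 9.6 and 14.2.4, relabel the current window and result as Year 1 / start of treatment Year 2.
2. Add a separate 2-year EDSS window centred on about Day 731 and report progression status at 2 years from it. The sponsor should set the limits so that an EDSS at a delayed Year 2 course start is not lost; an 18-month start at Day 549 already falls one day outside the present window.
3. Let the 2-year EDSS confirm worsening seen at the start-of-Year-2 score and, where a later EDSS was abstracted, let that confirm worsening first seen at 2 years. State a minimum interval close to 6 months and a maximum. The maximum must reach 731 − 365 = 366 days if the on-schedule 2-year score is to count. Report the distribution of actual intervals and keep the +91 to +272 rule as a sensitivity analysis.
4. Show unconfirmed progression and missing EDSS as separate groups.
5. Declare the change in SAP 7, and reconcile protocol 9.1.2.2, 9.3 and Table 1 on which EDSS scores are collected and used.

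At minimum, relabel the present result as progression first seen at about 1 year.

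**Cost.** SAP wording, some programming and a protocol clarification, with no new assessments. There are two drawbacks: many confirmation intervals will be about 12 months rather than 6, and scores after 2 years may not have been abstracted, since protocol 9.3 does not name them.

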9.7 Definition of On-treatment Period

Three different on-treatment periods will be defined based upon the induction period definition as follows:

Table 3. On-treatment periods

On-treatment period	Study day	
	From	To
Full effectiveness	84	Minimum of - Cut-off date - Date of death
Amplified effectiveness	56	
Full treatment	1	

9.8 Exposure time

Duration of exposure = date of last dose of cladribine – date of first dose of cladribine +1.

9.9 Follow-up time

Follow-up period is defined as follows:

- Follow-up: from date of last dose of cladribine until date of last contact (see Section 9.5).

9.10 Imputation of Missing Data

Unless otherwise specified, all data will be evaluated as observed, and no imputation method for missing values will be used. In all participant data listings, imputed values (e.g. partial dates) will be presented, and imputed information will be flagged.

Missing statistics, e.g. when they cannot be calculated, should be presented as “nd”. For example, if n=1, the measure of variability (SD) cannot be computed and should be presented as “nd”.

The following table for imputation rules for missing/partial dates will be considered:

Disease history	Incomplete dates for MS diagnosis will be imputed as follows: 
• If the day is missing, it will be imputed to the 15th day of the month.• If both day and month are missing and the year is prior to the year of cladribine initiation, the month and day will be imputed as July 1st.• If both day and month are missing and the year is same as the year of cladribine initiation, the month and day will be imputed as January 1st.• If the date is completely missing, no imputation will be performed.
Relapses	Start day of relapse:

	
• If the day is missing and the month and year are available, the day will be imputed to the first day of the month.• If the day and month are missing, the start date will be imputed to the 1st day of the available year. 
End date of the relapse:
 
• If the relapse is ongoing, the end date will be imputed to the date of last contact.• If the day is missing and the month and year are available, the missing day will be imputed to the last day of the month, if following the start date of relapse.• If both the day and month are missing, the end date will not be imputed.
Adverse events	Incomplete AE-related dates will be imputed as follows: 
• In case the onset date is partially missing but the onset month and year, or the onset year are equal to cladribine initiation then the onset date will be imputed by the minimum of cladribine initiation date and AE resolution date (if not missing).• In all other cases, the missing onset day or missing onset month will be imputed by 1.• Incomplete stop dates will be imputed by the last day of the month (if day is missing only), if not resulting in a date later than the date of participant's death. In the latter case, the date of death will be used to impute the incomplete stop date.• In all other cases, the incomplete stop date will not be imputed.
Previous and concomitant medication (including prior/subsequent DMTs)	Incomplete prior/concomitant medication (and DMT) start and stop dates will be imputed as follows: 
• If the medication start date is missing completely, then the medication start date will be replaced by the cladribine initiation date.• If the day of medication start date is missing, but the month and year are equal to the cladribine initiation date, then the medication start date will be replaced by the cladribine initiation date. For example, if the medication start date is --/JAN/2015, and cladribine initiation date is 15/JAN/2015, then the imputed medication start date will be 15/JAN/2015.• If both the day and month of medication start date are missing but the start year is equal to the cladribine initiation date, then the medication start date will be replaced by the cladribine initiation date. For example, if the medication start date is --/---/2014, and cladribine initiation date is

	
19/NOV/2014, then the imputed medication start date will be 19/NOV/2014.
 
• In all other cases the missing medication day or missing medication month will be replaced by 1. Incomplete stop date will be replaced by the last day of the month (if day is missing only), if not resulting in a date later than the date of participant's death. In the latter case the date of death will be used to impute the incomplete stop date.• In all other cases the incomplete medication stop date will not be imputed. 
In case an imputed medication start date is later than the medication stop date, it will be replaced by the medication stop date.

Dates of cladribine	
Start date of cladribine :
 
• If the day is missing and the month and year are available, the missing day will be imputed to the 15th of the month.• If both the month and day are missing and the year is available, and the end date is available for cladribine treatment Year 1 Week 2, cladribine initiation date will be imputed to the first day of the month prior to the date of Year 1 Week 2. For example, if the end date of week 2 is --/FEB/2019, the cladribine initiation date will be 01/JAN/2019. 
End date of cladribine :
 
• If the last date of cladribine is completely missing and no death date the participant should be considered to be ongoing and use the cut-off date for the analysis as the last dosing date• If the last date of cladribine is partially missing, then imputed last dose date is: = Last day of the month, if both Year and Month are available and Year = Year of min (discontinuation date, death date) and Month < the month of min (discontinuation date, death date)

10 Study Participants

The subsections in this section include specifications for reporting participant disposition and study discontinuations. Additionally, procedures for reporting protocol deviations are provided.

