8.2 Subgroup Definition and Parameterization

Subgroup analyses will be performed on primary and secondary outcomes. All subgroup analyses will be exploratory, no adjustment for multiplicity will be performed.

The following subgroups will be defined:

Most recent prior disease-modifying therapy:

- Naïve to disease-modifying therapies
- Prior platform therapy
- Prior high-efficacy cell-depleting treatment
- Prior high-efficacy non-depleting treatment

Prior and subsequent disease-modifying therapies will be medically reviewed on an ongoing basis and classified by the medical advisor. This process will be described in a separate document. DMTs classes will be linked with electronic case report form (eCRF) data for data analysis.

9 General Specifications for Data Analyses

Index date

Cladribine initiation date will be used as an index date to determine baseline and on-treatment periods.

Initial date

According to the protocol, data will be collected counting from 1 year prior to cladribine initiation date. The initial date will be calculated as follows:

- Initial date: Index date/cladribine initiation date - 1 (year).

All assessments occurred from initial date onwards will be considered for the analysis.

Pre-treatment period is defined as follows:

- Pre-treatment: from initial date until cladribine initiation date - 1 (day).

Listings

In the individual participant data listing all individual data will be listed as measured. Repeated measurements will be included in the listings. All listings will be sorted by subject ID, study period, and date of assessment as appropriate.

Tables and Descriptive Statistics

All data will be summarised by the most recent prior DMT group and overall. Repeated measurements (in the same time window) included in the listings will not be used for statistical analyses or summaries unless the repeated measurement was performed due to unreliable values/technical reasons.

Unless otherwise specified, continuous variables will be summarised using descriptive statistics, i.e. the number of participants with non-missing values (n), the number of participants with missing values, (nmiss), mean, standard deviation (SD), median, 25th percentile (Q1) and 75th percentile (Q3), minimum, and maximum. If there are no missing values, the number of participants with missing values should be indicated by a 0.

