9.2 Study Day

Day 1 is the day of cladribine initiation date (i.e. index date), the day before is Day -1 (no Day 0 is defined). Study day is defined relative to Day 1.

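### Relapse onsets with no recorded day are set to the first of the month, which misplaces relapses at initiation and at Day 84 and mainly affects the Day 1-365 and relapse-free analyses

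*SAP*

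**What the plan says.** Protocol 9.3 states that each relapse "will be recorded with the onset date (at least month and year", so a missing day is expected by design. The relapse row of SAP 9.10 then applies one rule: "If the day is missing and the month and year are available, the day will be imputed to the first day of the month". It has no condition on the initiation date. If the month is also missing, the onset becomes 1 January.

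Onset date alone decides the analysis year (Protocol 9.7.3; SAP 9.6, Table 1). The boundaries are:

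- SAP Section 9: "Pre-treatment: from initial date until cladribine initiation date - 1 (day".
- SAP 9.2: "Day 1 is the day of cladribine initiation date (i.e. index date".
- SAP 9.6: "Relapses occurred within the induction period window of 12 weeks (84 days) will not be included in the main analysis". Table 1 runs Year 1 from Day 84 to Day 365.
- SAP 9.6, on alternatives: "Sensitivity analyses will be repeated changing Year 1 interval to (56 to 365 days) and (1 to 365 days) respectively".

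Other rows of the SAP 9.10 table differ. For an adverse event with a partial date in the initiation month or year, "the onset date will be imputed by the minimum of cladribine initiation date and AE resolution date (if not missing". For a cladribine start date, "the missing day will be imputed to the 15th of the month"; MS diagnosis also goes to the 15th.

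**The concern.** The 1st is the earliest day a month-only onset can have, so the rule never moves an onset later. At a window boundary inside a month, every misplaced onset therefore crosses in the same direction. Two boundaries matter: initiation, which separates Year -1 from treated time, and Day 84, where the main Year 1 rate and the main relapse-free time begin.

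If the cladribine day is missing too, initiation becomes the 15th and a same-month relapse the 1st. That relapse is then always pre-treatment, whatever the true order.

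The planned alternative windows cannot reveal this, because they reuse the same imputed dates. The Day 1-365 analysis is there to show what leaving out the induction period does, yet it is the one that loses early post-initiation relapses to Year -1.

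**Working it through.** **The plan's own figure.** No figure in the documents sizes this point. The only precision figure is the half-width of 0.072 in Protocol 9.5. It reproduces as 1.96 × √(0.14 × 0.86 / 90) = 0.0717. It serves below only as a yardstick.

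**Inputs from the documents.** First-of-month rule (SAP 9.10); windows of Table 1 (SAP 9.6); Year 1 person-time of 281.25/365.25 for the main analysis and 1 year for Day 1-365 (SAP 14.1.1); rate 0.14 and 90 to 200 patients (Protocol 9.5).

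**Assumptions.** Initiation dates are spread evenly from 22 August 2017 to 30 September 2019 (770 dates). The end date is inferred from data collection ending in Q3 2023, a second review 1 year after enrolment, and initiation at least 3 years before enrolment. Rates are 1.0/year before initiation, r = 0.6 or 1.0/year from initiation to Day 84, and 0.14 after. All onset dates are month-only, which is the extreme case.

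**Example, initiation 12 March 2018 (Day 84 = 3 June 2018).**

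| True onset | True day | Imputed | Imputed day | Effect |
|---|---|---|---|---|
| 25 Mar 2018 | 14 | 1 Mar 2018 | -11 | induction to Year -1 |
| 20 Jun 2018 | 101 | 1 Jun 2018 | 82 | Year 1 to excluded |
| 20 Mar 2019 | 374 | 1 Mar 2019 | 355 | Year 2 to Year 1 |

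**Days of onset moved, averaged over the 770 dates.**

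| Boundary | First of month | 15th: back / forward |
|---|---|---|
| Day -365 | 14.59 out of Year -1 | 4.18 / 3.41 |
| Initiation | 14.59 into Year -1 | 4.18 / 3.41 |
| Day 84 | 14.72 into the excluded window | 4.23 / 3.46 |
| Day 365/366 | 14.63 from Year 2 into Year 1 | 4.20 / 3.41 |

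The exceptions are the 25 of 770 initiation dates on the 1st, where the imputed onset is Day 1, and the 25 where Day 84 is itself the 1st.

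**Main Year 1 rate (Day 84-365).** True: 282 × 0.14 / 281.25 = 0.1404. SAP rule: 0.1404 + (14.63 - 14.72) × 0.14 / 281.25 = 0.1403.

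**Day 1-365 rate.** True: (83r + 282 × 0.14) / 365.25 = 0.244 (r = 0.6) or 0.335 (r = 1.0). Change under the SAP rule: (14.63 × 0.14 - 14.59r) / 365.25 = -0.018 or -0.034, giving 0.226 or 0.301. The falls are 7.5% and 10.2%, each less than half of 0.072.

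**Year -1 rate.** True: 365 × 1.0 / 365.25 = 0.999. Change: 14.59 × (r - 1.0) / 365.25 = -0.016 at r = 0.6 (to 0.983) and 0 at r = 1.0. It rises only if relapses are more frequent just after initiation than a year before it.

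**Relapse-free analysis.** SAP 14.2.1 measures time as relapse date minus on-treatment start plus 1. An onset imputed before the start gives zero or negative time, and no handling is stated. Relapses affected, if all dates are month-only:

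- Day 84 start, at 0.14/year: 90 × 0.14 × 14.72 / 365.25 = 0.5; with 200 patients, 1.1.
- Day 1 start: 90 × 14.59r / 365.25 = 2.2 to 3.6; with 200 patients, 4.8 to 8.0.

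These are upper limits on patients lost as events, since a patient may relapse again later. A Kaplan-Meier estimate at a yearly mark draws in some onsets from just after that mark. The total number of patients with an event has no such gain at the end of follow-up.

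**The 15th instead.** Net changes come from the last column of the table:

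- Year -1: 0.999 + (-4.18 + 4.18 × 0.6 + 3.41 - 3.41) / 365.25 = 0.995 at r = 0.6.
- Day 1-365: 0.247 against 0.244 (r = 0.6); 0.334 against 0.335 (r = 1.0).
- Main Year 1: 0.146 (r = 0.6) or 0.151 (r = 1.0) against 0.140.

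**The case against.** The strongest reply is that the primary result barely moves. What the main Year 1 rate loses at Day 84 it regains from early Year 2, and initiation-month relapses lie outside that window however they are dated. The study tests no hypothesis, imputed dates are flagged in listings, and the share of month-only dates is unknown. At 0.14/year the rule moves at most about 0.5 relapses per boundary in 90 patients. Outside the initiation period, adverse event and medication start dates also default to 1. All of this stands.

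A reader might infer from the one-way shifts that the rule biases the primary outcome in favour of cladribine. The documents do not support that. The same rule removes onsets from Year -1 at Day -365, so the pre-treatment rate can fall, which works against an apparent benefit. No document says relapses are more frequent just after initiation than a year before it.

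A reader might also infer that relapses should get the adverse event rule. That would do more harm. About 14.9 days of true pre-treatment onset would be moved to Day 1. Combined with the 15th for other months, and with r = 0.6, it gives Year -1 0.957 (true 0.999) and Day 1-365 0.285 (true 0.244). Year-only onsets show the same problem. With initiation on 15 November 2018, 318 of the 365 days of 2018 (87%) precede treatment, so a pre-treatment date is usually right.

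The reply does not reach the Day 1-365 rate or the count of relapse events, and it gives no reason to prefer the 1st to the 15th.

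**Conclusion.** The point holds as a limited one. The first-of-month rule misplaces about 14.6 to 14.7 days of month-only onsets at initiation and again at Day 84. The main Day 84-365 rate is almost unaffected if the rate is flat after Day 84, and the direction for Year -1 is not determined. The consequence is a Day 1-365 rate about 8% to 10% too low, and relapse events that drop out of the relapse-free count or receive non-positive times.

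The percentages assume that all dates are month-only and that early rates are 0.6 to 1.0/year. They shrink in proportion to the actual share of month-only dates, and the rate effect vanishes if the rate is constant. This is worth correcting because the remedy is cheap, not because it threatens the main result.

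**What to change.** In the relapse row of SAP 9.10:

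1. Set a missing onset day to the 15th, no later than the relapse end date, and consistent with any chart evidence of whether the relapse came before or after initiation.
2. Do not move all initiation-month relapses to the initiation date, and do not add such a rule for year-only onsets in the initiation year.
3. Report how many relapse onsets are partial, by month-only and year-only.
4. Repeat the annualised relapse rate and relapse-free analyses with the earliest and the latest possible onset dates. For month-only dates the earliest is the current rule.
5. State how the relapse-free analysis treats an onset dated before the on-treatment start.

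The cost is a revised table row, a short addition to SAP 14.1.1 and 14.2.1, and reruns of existing programs. There is one small downside. If the rate is much higher before Day 84, the 15th lets slightly more induction-period relapses into the main Year 1 rate (0.146 to 0.151 against 0.140 if all dates are month-only). The earliest-date analysis would show this.
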